1.9 Dose Rationale and Risk/Benefits

No human trials have yet been undertaken to evaluate the use of glyburide in reducing edema in patients with intracerebral malignancies. In Thompson's study, the human dose equivalent of glyburide would be 2.5 mg/d for a 70 kg patient (2). No adverse mouse-related hypoglycemic events were noted with comparative levels of administration. Typical oral doses of glyburide in diabetic patients range from 2.5 to 20 mg/d. The starting dose is usually a single 2.5 mg tab/day, but this can be divided into twice-per-day administrations of 1.25 mg if patients are at risk of developing hypoglycemia. Human trials in ischemic stroke currently use the IV infusion form of glyburide (RP-1127), which has less potential for hypoglycemia and is not dependent on stomach pH. In a current phase I trial evaluating tolerability in healthy volunteers, RP-1127 is given as bolus followed by 72 hour continuous infusion. No serious adverse events have been reported. Two patients with persistent hypoglycemia (at 6 mg/d and 10 mg/d) were discontinued from the study, and one patient (at 6 mg/d) had a transient asymptomatic increase in aminotransferase/alanine aminotransferase levels. In this dose-finding study, 3 mg/d seemed the safest dose to yield therapeutic serum levels while minimizing hypoglycemic risk (12).

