3.2 Conditions for Patient Ineligibility

- 3.2.1** Known sulfonylurea treatment within 7 days prior to registration. Sulfonylureas include glyburide/glibenclamide (Diabeta, Glynase); glyburide plus metformin (Glucovance); glimepiride (Amaryl); repaglinide (Prandin); nateglinide (Starlix); glipizide (Glucotrol, GlibeneseR, MinodiabR); gliclazide (DiamicronR); tolbutamide (Orinase, Tolinsase); and glibornuride (Glutril).
- 3.2.2** Diffuse Leptomeningeal metastases.
- 3.2.3** Known allergy to sulfa or specific allergy to sulfonylurea drugs.
- 3.2.4** Use of VEGF inhibitors within 10 days prior to registration.
- 3.2.5** Allergy to gadolinium.
- 3.2.6** Type 1 diabetes mellitus or Type 2 diabetes mellitus actively receiving treatment.
- 3.2.7** Cognitive impairment that precludes a patient from acting as his or her own agent to provide informed consent.
- 3.2.8** Concurrent use of Bosentan.
- 3.2.9** Any major medical illnesses or psychiatric impairments that in the treating physician's opinion will prevent administration or completion of protocol therapy (which may include patients who are elderly, debilitated, or malnourished persons and/or those with renal, hepatic or adrenal insufficiency).
- 3.2.10** Pregnant or breast feeding women due potential damage to the fetus.
- 3.2.11** Inability to undergo MRI or SRS (e.g. due to safety reasons such as presence of a pacemaker).
- 3.2.12** Deemed by the treating physician to be unable to eat regular meals.

3.2.13 Patients currently on beta blockers.

3.2.14 Patient with a known diagnosis of ongoing alcoholism/alcohol abuse.

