5.4.2 Randomized Portion

5.4.2.1 All patients will be provided with a medication/blood glucose log, a blood glucose monitor, and taught to perform self fingerstick glucose draws (see Appendices II-VI). The first blood glucose draw will be done by a nurse or research team member on the visit 5-9 days prior to SRS and the initial value will be recorded in the blood glucose log.

5.4.2.2 If the Pilot Portion (at either full dose or at one dose reduction) demonstrates no "**serious toxicities**" and ≤ 3 "**concerning toxicities**" (described in section 5.3.1), patients in the Randomized Portion of the trial will be taught and instructed to measure blood glucose levels once a day (in the morning before breakfast (fasting)) starting at the initiation of the investigational medication and continuing for at least the first week after SRS. If no "**concerning toxicities**" or "**serious toxicities**" are found at the one week post SRS visit, then the patient may proceed through the rest of the trial with no further need to assess blood glucose via the fingerstick draws. If the patient does experience a "**concerning toxicity**" or "**serious toxicity**" then he/she must discontinue their investigational medication (as per section 5.3.2) and will not have to continue checking their blood glucose levels.

5.4.2.3 If the Pilot Portion (at either full dose or at one dose reduction) demonstrates no "**serious toxicities**" and 4-5 "**concerning toxicities**" (described in section 5.3.1), patients in the Randomized Portion of the trial will be taught and instructed to measure blood glucose as per section 5.4.1.

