7.4 Drug/Placebo Supply and Ordering

This protocol will use the Investigational Drug Services (IDS) pharmacy at UAB. The IDS pharmacy will be the only people unblinded to the study's investigational medication for the Randomized Portion of the study. The rest of the study team including treating physicians and patients will be blinded to the investigational medication.

Glyburide and the placebo will both be available by commercial/generic supply. Please note the placebo pill is not a sugar pill.

IDS will hold a supply of glyburide and placebo and dispense as appropriate when patients are enrolled on study. Once a patient is enrolled, a prescription for either glyburide or investigational medication will be faxed to the IDS pharmacy. Once the investigator has been verified by IDS, the drug will be dispensed. A sufficient supply of glyburide or investigational medication will be dispensed for the patient's entire study participation (beginning at least 5 days prior to SRS and continuing till the evening dose of the one month post SRS MRI scan). The investigational medication, when dispensed, will be packaged in a way that will keep the study team and patient blinded (for the Randomized Portion of the study). Once prepared by the IDS pharmacy the research team will be notified to retrieve the glyburide or investigational medication supply and take it to the patient.

7.4.1 In the event that a dose reduction is required for a patient who is currently on treatment in the Pilot Portion of the study (see Section 7.1) the following will occur. The patient will be notified and asked to return their supply of glyburide immediately. The IDS pharmacy will appropriately catalog (and if applicable destroy) the tablets per institutional guidelines. 0.75 mg glyburide tablets will then be dispensed for the patient. The study team will retrieve the new dose reduced supply of glyburide and provide it to the patient. Further dispensing of glyburide will be at this reduced dose by IDS unless otherwise notified by the study team.

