8.1 Permitted Supportive Therapy

All supportive therapy for optimal medical care will be given during the study period at the discretion of the attending physician(s) within the parameters of the protocol and documented in each site's patient charts as concomitant medication.

- 8.1.1** Anticonvulsants: Anticonvulsants may be used as clinically indicated. Doses at study entry and at specific time points of the treatment must be recorded.
- 8.1.2** Antiemetics: Prophylactic antiemetics may be administered at the treating physician's discretion.
- 8.1.3** Cytotoxic chemotherapy is permitted at the discretion of the treating physician(s).
- 8.1.4** All further therapy that is not included in Section 8.2 is permitted at the treating physician's discretion, but should be recorded.

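### Sulfonylureas are barred only before registration; afterwards one may be added to study drug that may be blinded glyburide, possibly with no scheduled home glucose checks running

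*Combined protocol and SAP*

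**What the plan says.** The only restriction on sulfonylureas is an entry criterion. Section 3.2.1 makes a patient ineligible for "Known sulfonylurea treatment within 7 days prior to registration" and lists the drugs meant. Section 3.2.6 excludes "Type 1 diabetes mellitus or Type 2 diabetes mellitus actively receiving treatment", which leaves untreated type 2 diabetes eligible. The glucose criterion in section 3.1.8 is a floor of 80 mg/dL with no ceiling.

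During the study, section 8.1.4 sets the default: "All further therapy that is not included in Section 8.2 is permitted at the treating" physician's discretion, with a duty to record it. Section 8.2 has one entry, corticosteroids given for cerebral edema. Section 4.2.9 stops study drug early for a dose limiting toxicity (DLT) or for a corticosteroid needed between registration and SRS, and for nothing else.

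On blinding in the randomized portion, section 7.4 says: "The rest of the study team including treating physicians and patients will be blinded to the investigational medication". Only the investigational pharmacy knows the arm.

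Home glucose checks in the randomized portion depend on the pilot result:
- With no serious and at most 3 concerning toxicities in the pilot, section 5.4.2.2 has patients check once daily until at least one week after SRS. If the one-week visit shows no such toxicity, "then the patient may proceed through the rest of the trial with no further need to assess blood glucose via the fingerstick draws".
- With 4 or 5 concerning toxicities, section 5.4.2.3 applies: "patients in the Randomized Portion of the trial will be taught and instructed to measure blood glucose as per section 5.4.1", and daily checks last until study drug stops.

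In both cases dosing continues to the evening of the one-month MRI.

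**The concern.** The sponsor wanted patients free of other sulfonylureas at entry, and section 1.8 names hypoglycemia as the most common side effect of glyburide. The same reason for caution holds throughout dosing, yet the written rules turn from excluding these drugs to permitting them once the patient is registered. This is more than a missing detail, because section 8.1.4 expressly permits whatever section 8.2 does not list.

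Two routes are open in the text. A patient with untreated type 2 diabetes may enter and then need treatment. Or a patient may start a corticosteroid after SRS: this counts as a treatment failure under section 8.2.1 but does not stop study drug, and section 1.8 says dexamethasone disturbs glucose metabolism in approximately 50% of patients. In either case the physician might prescribe a sulfonylurea to someone already on blinded glyburide. Under section 5.4.2.2 this could happen with no scheduled glucose measurement until the one-month visit. What is at stake is patient safety, not the efficacy comparison.

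**Working it through.** The plan gives no figure on this point, so there is none to reproduce. The check has three parts.

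**1. Is there a bar after registration?**
- Section 3.2.1: applies to the 7 days before registration only.
- Section 8.2: corticosteroids for cerebral edema only.
- Section 8.1.4: everything else permitted, to be recorded.
- Section 8.1: care stays within the protocol's parameters, but no parameter restricts sulfonylureas on study.
- Section 4.2.9: starting a sulfonylurea does not stop study drug.

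There is no bar from registration onward. The pilot rules leave the same opening (section 4.1.9 is parallel to 4.2.9), but the pilot is open-label and has at least daily checks to the end of dosing.

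**2. How long can dosing run without scheduled home checks, if section 5.4.2.2 applies?**
Inputs: one-week visit on day 7 ± 3 (section 4.2.6), so days 4 to 10; one-month MRI on day 30, -5 or +10 (section 4.2.7 and Appendix VIII), so days 25 to 40; checks to last at least one week after SRS (sections 4.2.5.2 and 5.4.2.2, and Appendix VIII, randomized portion, note 3).

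Gap = MRI day - the later of day 7 and the one-week visit day.
- Nominal: 30 - 7 = 23 days.
- Shortest: 25 - 10 = 15 days.
- Longest: 40 - 7 = 33 days.
- If a day-4 visit ends the checks under section 4.2.6.4, against the one-week minimum: 40 - 4 = 36 days.

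These are upper bounds on unmonitored overlap, reached only if the second drug starts no later than the end of checks. The documents give no start day. For an assumed start on day d after SRS, nominal unmonitored overlap = 30 - max(d, 7):

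| Assumed start day | Overlap (days) |
|---|---|
| 7 | 23 |
| 14 | 16 |
| 21 | 9 |
| 28 | 2 |

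**3. What total dose would result?**
This assumes the added drug is glyburide at the usual start in section 1.9: "The starting dose is usually a single 2.5 mg tab/day".
- Trial dose: 2 × 1.25 = 2.5 mg/d. Total: 2.5 + 2.5 = 5 mg/d, which is 5 / 2.5 = 2 times the trial dose.
- Reduced trial dose: 2 × 0.75 = 1.5 mg/d. Total: 1.5 + 2.5 = 4 mg/d.
- Section 1.9 also says: "Typical oral doses of glyburide in diabetic patients range from 2.5 to 20 mg/d". At full trial dose the total passes 20 mg/d only if more than 20 - 2.5 = 17.5 mg/d is added.

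**The case against.** The best reply is that this is unlikely and partly covered. The physician is blinded to the arm, not to the trial; anyone who knows the patient may be on glyburide would have to disregard that to add a sulfonylurea. Patients on treatment for diabetes are excluded. Section 8.2.1 limits steroids to symptomatic patients with imaging evidence of increasing edema who are judged to need them. Added therapy must be recorded, so the study team can see it. Appendix II tells patients to check more often with symptoms or when medicine doses change, and they keep the meter. Low blood sugar intervention and DLT stopping remain. Section 7.6 allows approved unblinding in a life-threatening event or extraordinary circumstance, after which study drug stops.

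Most of this stands, and it makes the event less likely and an episode milder or shorter. But recording follows the prescription, the glucose measures act after a reading or symptom, routine treatment of raised glucose does not clearly qualify for unblinding, and reliance on the physician's caution is not a rule. None of it bars the co-prescription.

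A reader might infer three stronger things that the documents do not support:
- *That half of steroid-treated patients would need a sulfonylurea.* The 50% figure covers any glucose disturbance on dexamethasone. It is not a rate of drug-treated hyperglycemia, and nothing says a sulfonylurea would be chosen.
- *That the combined dose is shown to be harmful.* The example totals lie within the range section 1.9 gives for diabetic patients. The persistent hypoglycemia it reports at 6 and 10 mg/d arose in healthy volunteers on intravenous bolus plus infusion, a different setting.
- *That blinding creates the gap.* The missing bar comes from sections 8.1.4 and 8.2 and exists in the open-label pilot too. Blinding only removes the prescriber's knowledge of the arm.

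**Conclusion.** The point holds as a safety gap in the text: after registration the protocol permits a second sulfonylurea on top of study drug. In the randomized portion this can happen without the prescriber knowing the arm and, if section 5.4.2.2 applies, with a nominal 23 days of dosing left and no scheduled home checks (15 to 33 days honoring the one-week minimum). If section 5.4.2.3 applies, checks continue and the monitoring part falls away.

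A reader might go on to infer a threat to the primary comparison. The documents give no basis for that: no sample size, power or error rate depends on this. They also give no frequency of sulfonylurea starts and no measure of harm. The overlap days rest on assumed start days and describe exposure time, not probability or severity. Consent pages and some other text are not in the public copy and could not be checked. The textual gap is certain and the harm scenario is only possible, so this is an improvement the sponsor could make, not a defect that must be repaired.

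**What to change.** Add to section 8.2, for both portions, that the drugs listed in section 3.2.1 are not permitted from registration through the last dose of study drug. Starting the bar at registration also covers the interval to first dose, which otherwise stays open. State the handling:
- **Needed after SRS:** stop study drug and keep the patient evaluable in the randomized arm, as section 5.3.2 does for a DLT and in line with the as-randomized rule in section 9.1.2.
- **Needed after registration but before SRS:** stop study drug and treat the patient as inevaluable and replaced, consistent with sections 7.2.3 and 4.2.9.2.
- **Any other glucose-lowering drug started:** resume daily home glucose checks until study drug ends.

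The cost is a few lines of text. A few patients would stop study drug early, use another agent, or go back to fingersticks with the meter they already have. Replacing a patient before SRS may remove someone already randomized, but the protocol's existing pre-SRS rules already do that.

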8.2 Non-Permitted Supportive Therapy

- 8.2.1** Corticosteroids: Dexamethasone (or any other corticosteroid whose purpose is to treat cerebral edema) should only be administered if the patient is clinically symptomatic, has imaging demonstrating increasing cerebral edema, and is deemed by the treating physician to require dexamethasone (or another corticosteroid). If administered between SRS and the one month follow-up MRI, these patients will be recorded as a treatment failure (primary endpoint). If initiated prior to SRS, this is criteria for withdrawal from the protocol, these patients would be deemed inevaluable. If initiated after the one month follow-up MRI, the dose, value, and reason will be recorded. Low dose prednisone or other non-dexamethasone steroids are allowed as long as they are not administered with the intent of treating cerebral edema.

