4.2.9 Conditions for early patient stopping of investigational medication

4.2.9.1 A dose limiting toxicity (DLT) is reached. See section 5.3.2.

4.2.9.2 Patient requires corticosteroid administration after registration but prior to SRS, please note these patients will be deemed inevaluable.

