5.2 Randomized Portion

The Randomized Portion of this study will only proceed if there have been 10 evaluable patients on the Pilot Portion (this includes both full dose glyburide and reduced dose glyburide, if applicable) and it is deemed safe. All data will be reviewed and approved by the Data Safety Monitoring/Quality Assurance Committee (DSMQAC) after the Pilot Portion and prior to starting the Randomized Portion at the safe dose as determined by the Pilot Portion. The Randomized Portion will enroll 40 evaluable patients. Inevaluable patients will be replaced.

Patients with brain metastases, who are not taking dexamethasone (or any other corticosteroid with the purpose of treating cerebral edema) within 5 days prior to SRS, after informed consent, will be randomized to a blinded investigational medication:

- Non-Micronized glyburide (1.25 mg po BID) should begin at least 5 days prior to SRS to be taken until the evening dose on the day of the one month follow-up MRI.
OR
- Placebo (1 tablet po BID) should begin at least 5 days prior to SRS to be taken until the evening dose on the day of one month follow-up MRI.

All patients will receive linac-based radiosurgery, which must be initiated at least 5 days after starting the investigational medication (can be more for patients being treated with linac-based radiosurgery where the MRI may be done within 21 days prior to SRS treatment).

For treatment planning and at the time of the one and three month follow-up appointments, the patient must undergo a brain MRI with and without contrast. T1-weighted, T2, and/or

FLAIR MRI of the brain (maximum slice thickness 5mm). FLAIR imaging is preferred. The treatment planning MRI may be done within 21 days prior to SRS treatment only for patients being treated with linac-based radiosurgery where it is not standard of care to complete a MRI on the day of SRS (as it is with gamma knife).

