Appendix VII for Adverse Event (AE) definitions and grading scale information.

If multiple toxicities are seen, the presence of a DLT should be based on the most severe toxicity experienced. Any patient who achieves a DLT will be taken off of the investigational medication immediately, but will still be evaluable.

Concerning Toxicity

1. Any **asymptomatic grade 3 or 4 hypoglycemia** as defined by CTCAE version 4.0.
2. Any **non-hematologic grade 3 or greater toxicity** (including neurologic toxicity) that is associated with a blood glucose level ≤ 80 mg/dl and is resolved with "low blood sugar intervention" (e.g. a return of blood glucose level to ≥ 80 mg/dl).

Serious Toxicity

1. Any **grade 5 toxicity** that is deemed by the investigator to be **at least possibly attributable to the investigational medication**.
2. Any **symptomatic grade 3 or 4 hypoglycemia** that is associated with a **non-hematologic grade 3 or greater toxicity** that is not resolved with “low blood sugar intervention” (e.g. does not return to blood glucose level of ≥ 80 mg/dl) that is deemed by the investigator to be **at least possibly attributable to the investigational medication**.

Investigational medication will be discontinued for any patient that meets the criteria for a “concerning toxicity” or “serious toxicity”. These patients will still be evaluable. All other patients currently on treatment at the time may continue with their current investigational medication without interruption.

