7.2 Randomized Portion

7.2.1 Non-Micronized glyburide (1.25 mg po BID) or placebo (1 tablet po BID) should be administered orally twice a day beginning at least 5 days prior to SRS. The investigational medication will be taken in the morning with breakfast and in the evening with dinner. All patients and the study team will be blinded to the investigational medication which will continue until the evening dose on the day of the one month post SRS follow-up MRI. If the patient misses a dose at any time, it will not be made up. All doses (whether missed or taken) should be recorded in the medication administration log.

7.2.1.1 In the event of a DLT in the Pilot Portion requiring a dose reduction and this dose is considered safe, patients will receive either a reduced dose of non-micronized glyburide (now at 0.75 mg po BID) or the placebo (1 tablet po BID). The investigational medication will be taken in the morning with breakfast and in the evening with dinner. All patients and the study team will be blinded to the investigational medication which will continue until the evening dose on the day of the one month post SRS follow-up MRI. If the patient misses a dose at any time, it will not be made up. All doses (whether missed or taken) should be recorded in the medication administration log.

7.2.2 In the event of a DLT in the Randomized Portion of the study, the patient who experienced the DLT will stop their investigational medication immediately. Other patients currently on study at the time of the DLT will continue on study treatment without interruption.

7.2.3 If a patient suffers a DLT (either a “*concerning toxicity*” or a “*serious toxicity*”) after registration but before SRS, he/she will be removed from the protocol and considered inevaluable.

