9.0 STATISTICAL CONSIDERATIONS

9.1 Definition of primary outcome/endpoint

9.1.1 Pilot Portion: Occurrence of Dose Limiting Toxicities (DLTs) between the time of glyburide initiation and the time of the one month follow-up MRI.

9.1.2 Randomized Portion:

Each eligible patient will be evaluated for treatment outcome as success or failure, as defined later in this section. Each patient's treatment outcome will be associated with randomized regimen regardless of the treatment the patient actually receives. A treatment failure will be considered to have occurred if edema increases sufficiently to require the initiation of dexamethasone (or any corticosteroid administration with the purpose of treating cerebral edema) between the time of SRS* and the time of the one month follow-up MRI, or the patient dies in that same interval from a cause considered probably or likely related to Glyburide. Otherwise, the patient will be considered to have experienced treatment success.

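### Randomized portion: a DLT before SRS is both inevaluable and still evaluable, and steroid starts before SRS are dropped and replaced after randomization

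*Combined protocol and SAP*

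**What the plan says.** Section 4.2.4.1 places randomization no later than the visit 5-9 days before SRS. Section 5.2 adds: "Non-Micronized glyburide (1.25 mg po BID) should begin at least 5 days prior to SRS". Once drug has started, the interval before SRS is both after randomization and on assigned treatment.

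**Steroids.** For a steroid given for edema before SRS, 8.2.1 says: "If initiated prior to SRS, this is criteria for withdrawal from the protocol, these patients would be deemed inevaluable". Section 4.2.9.2 has a similar rule, not limited to edema: "Patient requires corticosteroid administration after registration but prior to SRS, please note these patients will be deemed inevaluable". After SRS, 8.2.1 treats the event as an outcome: "If administered between SRS and the one month follow-up MRI, these patients will be recorded as a treatment failure (primary endpoint").

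**DLTs.** Section 7.2.3 says that a patient with a DLT "after registration but before SRS, he/she will be removed from the protocol and considered inevaluable". Section 5.3.2, and 7.3.4 in the same words for the randomized portion, say: "Any patient who achieves a DLT will be taken off of the investigational medication immediately, but will still be evaluable".

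**Analysis set.** Section 5.2: "The Randomized Portion will enroll 40 evaluable patients. Inevaluable patients will be replaced". Section 9.1.2: "Each eligible patient will be evaluated for treatment outcome as success or failure, as defined later in this section". It then assigns each outcome to the randomized regimen whatever treatment was received, and scores as success anyone who does not meet the failure definition. Section 9.3.2 triggers the analysis at 20 randomized patients per regimen. Section 9.5.2 allows for up to 20% inevaluable.

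**The concern.** For a DLT before SRS, two careful analysts could follow the plan and produce different primary analysis sets. One removes and replaces the patient under 7.2.3. The other keeps the patient under 5.3.2 and 7.3.4.

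For steroids the text gives one answer, but it removes patients after randomization because of something that happened on study drug. Glyburide is being tested because it might reduce edema and so the need for steroids, and the DLT definitions are largely built on hypoglycemia. Assigned arm may therefore influence who reaches the analysis. Blinding limits differential judgement, but it does not stop events that the drug causes or prevents. At stake is a single go/no-go decision at one-sided p ≤ 0.30 with 20 patients per arm, where a few selectively removed patients can matter.

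**Working it through.** **1. The plan's own figures.** Inputs: 20 per arm, exact test, one-sided p ≤ 0.30 (9.3.2); success 50% on placebo and 75% on glyburide, power 0.80 (9.5.2). I took the exact test to be Fisher's and summed the two binomial distributions over all outcomes with p ≤ 0.30. In practice this means glyburide leads by three or more successes (a lead of two suffices only at 2 v 0 and 20 v 18).

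- 75% v 50%: 0.802, which reproduces the stated 0.80.
- 50% v 50%: 0.215, the actual chance of a go with no drug effect (false-go).
- Enrollment: (10 + 40)/0.80 = 62.5, rounded up to 63, as stated. For the randomized portion alone, 40/0.80 = 50, so about 10 randomized patients could be replaced for all reasons together.

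**2. The DLT texts side by side.** Section 7.2.3 turns on timing (before SRS) and gives inevaluable. Sections 5.3.2 and 7.3.4 cover any DLT, have no timing exception and do not refer to 7.2.3. Section 4.2.9 lists DLT and pre-SRS steroid together, attaches inevaluable only to the steroid, and for DLT points to 5.3.2.

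**3. Selective loss with no drug effect.** The drop rates are assumptions; the documents give none. Let failure be f = 0.50 among all randomized patients in each arm, let a fraction d be dropped before SRS, and let all of those be would-be failures. Replacement restores 20 per arm. Success among the analysed is 1 − (f − d)/(1 − d) = 0.50/(1 − d).

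| d in the arm losing more (the other arm loses d/2) | Success in that arm | Success in the other arm | False-go, placebo loses more | False-go, glyburide loses more | False-go, both lose d |
|---|---|---|---|---|---|
| 5% | 0.526 | 0.513 | 0.190 | 0.241 | 0.214 |
| 10% | 0.556 | 0.526 | 0.164 | 0.272 | 0.213 |
| 20% | 0.625 | 0.556 | 0.105 | 0.361 | 0.207 |

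**4. Scoring of DLT patients kept in the analysis.** Suppose a fraction e of glyburide patients only has a DLT before SRS, receives no SRS and starts no edema steroid (assumed e = 5/10%), with placebo success 50%. With p = 0.50 (no effect) or 0.75 (planned effect), glyburide success becomes p(1 − e) if they are scored as failures and e + p(1 − e) if scored as successes.

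- Failure: false-go 0.171/0.134, power 0.721/0.631.
- Success: false-go 0.264/0.318, power 0.826/0.849.

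The choice of scoring matters, and 9.1.2's default to success would make it unannounced.

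**The case against.** **The steroid rule can be read as consistent.** Section 3.1.5 makes freedom from edema steroids from 5 days before SRS an eligibility condition, and 9.1.2 analyses eligible patients. A reader might infer that the exclusion contradicts the by-randomized-regimen rule; on this reading it does not. This stands. What remains is that eligibility is then settled by an event after randomization and on drug.

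**The DLT rule may be a deliberate exception.** The pilot portion has the same pairing (7.1.4 against 5.3.1). That is possible, but no section signals it and 4.2.9 does not follow it.

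**There may be no bias.** If dropped patients would otherwise have fared like those who stayed, the evaluable comparison keeps 0.215 and 0.802 even with unequal losses. Equal losses with no drug effect also change almost nothing. The window is short, and losses between registration and randomization cannot depend on arm. All of this stands.

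**Stronger readings that the documents do not support:**

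- That the current rule cannot register any drug effect before SRS. The baseline MRI may be up to 21 days before SRS (4.2.3, 8.3.3), hence before first dose, so FLAIR change in analysed patients can span that period. Section 9.4's limit to evaluable patients excepts graded toxicities, and 7.3.3 follows withdrawn patients for adverse events for 30 days after last dose.
- That deleting the word inevaluable would turn every early steroid start into a success. Section 8.2.1 counts steroids administered after SRS, so a patient still on steroid then could be a failure.
- That 20 randomized per regimen against 40 evaluable is a second defect. The enrollment arithmetic shows an evaluable-based design, so this is loose wording.

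**Conclusion.** The point holds and should be fixed before unblinding. The DLT contradiction is in the text and needs reconciling whatever the event rate. The steroid exclusion is a weakness of the analysis population, not a contradiction.

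Neither the size nor the direction of any bias can be stated from the documents. DLT losses would be expected mainly on glyburide, while steroid losses could fall more on placebo. In the illustration false-go runs from 0.105 to 0.361 around 0.215, but both extremes need 20% of one arm and 10% of the other to be dropped, all of them would-be failures. At 5% the range is 0.190 to 0.241. A reader might infer that the stated power is wrong; it is correct for 20 evaluable patients per arm.

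**What to change.** These changes concern analysis only; clinical management, including stopping of study drug, stays as written.

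1. Reconcile 7.2.3 with 5.3.2 and 7.3.4 for the randomized portion. Patients with a DLT after randomization and before SRS stay in the primary analysis by assigned arm and are not replaced. For any who receive no SRS and start no edema steroid, pre-specify one scoring that decides the p ≤ 0.30 rule (failure, for example, is conservative), and show the other as sensitivity.
2. Report by arm the exclusions for edema steroids started after randomization and before SRS, and the cancellations under 6.1. Pre-specify an all-randomized analysis by assigned arm that counts such steroid starts as treatment failure, and report it beside the evaluable-only result. If it is made primary instead, change 3.1.5, 4.2.9.2, 8.2.1 and 9.1.2 (the eligible-patient wording and the default to success) together.
3. Align the wording of 9.3.2 with the 40 evaluable patients of 5.2.

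**Cost.** One-month steroid and MRI data are needed for a few patients now withdrawn (Appendix VIII marks that MRI as conventional care), plus a little extra analysis. Scoring no-SRS DLT patients as failures lowers power to 0.721/0.631 if 5/10% of glyburide patients only are affected (assumed).

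Making the all-randomized analysis primary is a harder choice, because some early starts may be failed tapers. With early failures added to the planned rates, success is (1 − e) times the planned rate. At 20 per arm and assumed e = 5/10/20%, power is 0.774/0.746/0.689 if early failures are equal, 0.811/0.820/0.839 if glyburide has half the placebo rate, and 0.748/0.690/0.567 in the reverse case. That is why item 2 asks for it alongside the evaluable-only result.
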